2.3. Study Design

This Phase 2, randomized, double-blind, study will evaluate the efficacy and safety of nirmatrelvir/ritonavir (5-, 10-, and 15-day dosing durations) for the treatment of COVID-19 in approximately 150 nonhospitalized symptomatic participants aged at least 12 years and weigh \geq 40 kg who are immunocompromised (main study population). In addition, this study will also evaluate the efficacy and safety of a second treatment course of nirmatrelvir/ritonavir (5-, 10-, or 15-days) in an additional population of nonhospitalized symptomatic participants who are immunocompromised with a rebound in COVID-19 within 14 days following completion of an initial 5-day treatment course of nirmatrelvir/ritonavir (population with rebound).

Participants in the additional population with rebound will be recruited during the enrollment phase for the main study population. Enrollment of the population with rebound will stop after the main study population is fully enrolled or after 50 participants in the population with rebound have been enrolled, whichever occurs sooner.

Eligible participants (main study population and additional population with rebound) for this study will be randomly assigned (1:1:1) to receive:

- nirmatrelvir plus ritonavir orally q12h for 5 days followed by placebo for nirmatrelvir plus ritonavir q12h for 10 days; or
- nirmatrelvir plus ritonavir orally q12h for 10 days followed by placebo for nirmatrelvir plus ritonavir q12h for 5 days; or
- nirmatrelvir plus ritonavir orally q12h for 15 days.

[figure not shown]
Participants will be screened on the same day as randomization or 1 calendar day before randomization. For the main study population, enrollment of participants considered immunocompromised based solely on receiving corticosteroids or TNF blockers will be capped at approximately 25%. Enrollment of participants considered immunocompromised based solely on receiving corticosteroids or TNF blockers in the additional population with rebound will not be capped.

For the main study population, randomization will be stratified by those who are considered immunocompromised solely based on corticosteroids or TNF blocker use (yes/no; see Protocol Section 10.9.4 Point #4). Randomization for the population with rebound will not be stratified by those who are considered immunocompromised solely based on corticosteroids or TNF blocker use.

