The total study duration is up to 24 weeks, including study intervention administration through Day 15 or Day 16, safety assessments through Day 44, efficacy assessments through Week 24, and long-term follow-up at Weeks 12 and 24.

DMB02-GSOP-RF02 7.0 Statistical Analysis Plan Template 31-Jan-2022 PFIZER CONFIDENTIAL TMF Doc ID: 98.03 Page 10 of 32

Figure 1. C4671034 Study Design

Analyses will be conducted after the main study population is fully enrolled and have completed the Day 44 visit regardless of the number of randomized participants in the population with rebound. There will be 2 analysis time points for reporting the results of this study. The primary analysis will be performed after all participants in the main study population have completed the Day 44 visit. The follow-up analysis will be performed after all participants in the main study population have completed the Week 24 visit. In addition, both analyses (primary and follow-up) will include separate results for the main study population and the additional population with rebound.

An independent E-DMC will review unblinded data to ensure the safety of participants on an ongoing basis throughout the duration of the study.

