2.4. Sample Size Determination

Up to approximately 200 participants will be enrolled in this study.

The study will randomize approximately 150 participants in a 1:1:1 randomization ratio, resulting in approximately 50 participants in each treatment arm (main study population). In addition, the study will also enroll up to 50 additional nonhospitalized symptomatic participants (in a 1:1:1 randomization ratio) who are immunocompromised with a rebound in COVID-19 within 14 days following completion of an initial 5-day treatment course of nirmatrelvir/ritonavir (population with rebound).

Analyses will be conducted after the main study population is fully enrolled and have completed the Day 44 visit regardless of the number of randomized participants in the population with rebound. There will be 2 analysis time points for reporting the results of this study. The primary analysis will be performed after all participants in the main study population have completed the Day 44 visit. The follow-up analysis will be performed after all participants in the main study population have completed the Week 24 visit. In addition, both analyses (primary and follow-up) will include separate results for the main study population and the additional population with rebound.

As no formal hypothesis testing will be performed for this study, no power calculation was carried out to assess the number of participants required for each treatment arm. For the main study population, the goal of the primary analysis is to estimate the treatment effect for each duration of nirmatrelvir/ritonavir. The smaller numbers of participants in these groups will be reflected in the precision of the estimate of the primary endpoint. Table 2 displays which effect sizes would be excluded based on the expected width of the confidence interval around

DMB02-GSOP-RF02 7.0 Statistical Analysis Plan Template 31-Jan-2022 PFIZER CONFIDENTIAL TMF Doc ID: 98.03 Page 11 of 32 the estimate of the proportion of participants with sustained NP swab SARS-CoV-2 RNA <LLOQ (defined as <2.0 log₁₀ copies/mL) from Day 15 through Day 44 with a sample size of 50.

When the proportion of participants with sustained NP swab SARS-CoV-2 RNA <LLOQ from Day 15 through Day 44 ranges from 0.1 to 0.5, Table 2 displays the precision (width of the confidence interval) for the respective proportion to be estimated with a sample size of 50. That is, the width of the 95% CI does not exceed 14%.

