6.1.1. Main Analysis

The primary descriptive analysis will summarize, separately for the main study population and the population with rebound, the number and proportion of participants with sustained NP swab SARS-CoV-2 RNA <LLOQ (defined as <2.0 log₁₀ copies/mL) from Day 15 through Day 44 for each treatment arm in the Evaluable Analysis Set and FAS. Participants DMB02-GSOP-RF02 7.0 *Statistical Analysis Plan Template* 31-Jan-2022

> PFIZER CONFIDENTIAL TMF Doc ID: 98.03 Page 16 of 32

receiving non-study antiviral or monoclonal antibody therapy post-baseline (between randomization and Day 44 visit) for the treatment of COVID-19 will be considered as not achieving sustained NP swab SARS-CoV-2 RNA <LLOQ in the primary analysis.

As viral load measurements from NP swabs are taken on Days 15, 21, 28, 35, and 44 during the time interval from Day 15 to Day 44, all of the measurements that are non-missing must be <LLOQ (including undetectable), and the Day 15, Day 44, and no more than one of the Day 21, 28, and 35 measurements can be missing in order for the event to be considered sustained.

In addition, 95% CIs for the proportion of participants with sustained NP swab SARS-CoV-2 RNA <LLOQ from Day 15 through Day 44 for each treatment arm will be calculated using binomial distribution normal approximation. The difference in proportions for the primary endpoint and associated 95% CI will be calculated for each pairwise comparison of the treatment arms.

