6.3. Subset Analyses

Subgroup analysis will be performed for the main study population as numbers permit and results will be summarized only. Subgroup analyses of the primary endpoint will include:

- age group (<65, ≥ 65 and <18; ≥ 18);
- Sex (Male, Female);
- Race (White, Black or African American, Asian, Other);
- Ethnicity (Hispanic/Latino, Not Hispanic/Latino);
- BMI category (<25, 25-29, ≥30);
- Immunocompromised Category (stratification factor*): Participants considered immunocompromised based solely on receiving corticosteroids or TNF blockers (yes/no)
- Baseline viral load defined as: $< 10^4$ copies/mL vs $\ge 10^4$ copies/mL
- Baseline viral load defined as: $< 10^7$ copies/mL vs $\ge 10^7$ copies/mL);
- Duration since first symptom (<= 5 days, > 5 days <= 30, >30)
- Vaccination status (unvaccinated or received last vaccination more than 6 months prior to randomization vs received last vaccination within 6 months prior to randomization)
 - *: Participants will be analyzed according to the category as determined by the CRF data and not according to the category selected at randomization (when different).
 - Subgroup analysis is not planned for the population with rebound, but may be performed if numbers permit.

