8. APPENDICES

Endpoint	Analysis Type	Population	Data Inclusion and Rules for Handling Intercurrent Events and Missing Data	Analysis Model
Proportion with sustained SARS- CoV-2 RNA < LLOQ from Day 15 to Day 44 (NP)	Primary	Evaluable, FAS	Intercurrent event: non-study anti- viral or mAb therapy – participant considered failure No imputation of missing data	Descriptive (n, %), 95% CI for proportion and the difference in proportion using binomial distribution normal approximation
Proportion with sustained SARS- CoV-2 RNA < LLOQ from Day 15 to Day 44 (NP)	Supplementary	Evaluable	Intercurrent event: non-study anti- viral or mAb therapy – data excluded/considered missing No imputation of missing data	Descriptive (n, %), 95% CI for proportion and the difference in proportion using binomial distribution normal approximation
Proportion with sustained SARS- CoV-2 RNA < LLOQ from Day 15 to Day 44 (NP)	Supplementary	Evaluable	Intercurrent event: non-study anti- viral or mAb therapy – data included as is No imputation of missing data	Descriptive (n, %),95% CI for proportion and the difference in proportion using binomial distribution normal approximation
Proportion with sustained SARS- CoV-2 RNA < LLOQ from Day 15 to Day 44 (NP)	Supplementary	Evaluable	Participants with baseline SARS- CoV-2 RNA level <lloq be
excluded Intercurrent event: non-study anti- viral or mAb therapy – participant considered failure</lloq>	Descriptive (n, %), 95% CI for proportion and the difference in proportion using binomial distribution

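### Normal-approximation 95% CIs for the primary endpoint cover about 91% on average in rebound arms of 17 or fewer, and collapse to zero width at 0% or 100%

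*SAP*

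**What the plan says.** Protocol 9.3.2.2 asks for 95% CIs for each arm's proportion and for each pairwise difference, but names no method. The SAP does. Under 6.1.1 the single-arm intervals "will be calculated using binomial distribution normal approximation". The primary row of Appendix 1 extends this to the comparison: "95% CI for proportion and the difference in proportion using binomial distribution normal approximation". No continuity correction, exact or score alternative, or rule for 0% or 100% observed is given.

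The method applies to both populations: "The primary descriptive analysis will summarize, separately for the main study population and the population with rebound". For the size of the second population, SAP 2.3 says "Enrollment of the population with rebound will stop after the main study population is fully enrolled or after 50 participants" have entered, whichever comes first, and that analysis proceeds "regardless of the number of randomized participants in the population with rebound". SAP 2.4 gives 1:1:1 allocation in both populations and about 50 per arm in the main one. SAP 5.1 rules out formal hypothesis testing, and SAP 5.3 says missing endpoint data are not imputed and reduce N.

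**The concern.** The Wald interval takes its standard error from the observed proportion. In a small sample that makes it too short when the observed proportion is near 0 or 1, and gives it no length at all when every participant, or none, responds. The design makes small arms certain in the rebound population: the cap allows at most about 17 per arm, and there is no floor.

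Because nothing is tested and no power calculation was done, the intervals are all the reader gets as a formal measure of uncertainty. A rebound arm in which all or none clear the virus would appear in the primary-endpoint table with a nominal 95% interval that claims perfect certainty. If two arms both sat at such an extreme, the interval for their difference would also have zero width.

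**Working it through.** **Inputs.** Two-sided 95%, z = 1.96 (SAP 6.1.1). Rebound: 50/3 = 16.7, so at most about 17 per arm (SAP 2.4). Main: about 50 per arm (SAP 2.4). SAP 2.4 considers true proportions where the value "ranges from 0.1 to 0.5, Table 2 displays the precision"; since coverage is symmetric about 0.5, this is equivalent to 0.1 to 0.9. No expected rebound rate is given. An arm of 10 (30 rebound participants) is added as an assumption.

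**The plan's own figures.** 1.96·√(p(1−p)/50) at p = 0.1, 0.2, 0.3, 0.4, 0.5 gives 0.083, 0.111, 0.127, 0.136, 0.139. These match all five entries of SAP Table 2, which confirms that the Wald interval is meant. They are half-widths, although the table labels them widths; the full widths run from 0.166 to 0.277. That labelling is a separate matter.

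**Formulas.** Wald: p̂ ± z·√(p̂(1−p̂)/n). Wilson: [p̂ + z²/(2n) ± z·√(p̂(1−p̂)/n + z²/(4n²))] / (1 + z²/n). Exact coverage at p is the sum of Binomial(n, p) probabilities over the counts whose interval contains p; there is no simulation. Averages are over 801 equally spaced p from 0.1 to 0.9. The chance of zero width is pⁿ + (1−p)ⁿ.

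**Single-arm coverage (%), Wald / Wilson**

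| True p | n = 10 (assumed) | n = 17 | n = 50 |
|---|---|---|---|
| 0.1 or 0.9 | 65.0 / 93.0 | 82.9 / 97.8 | 87.9 / 97.0 |
| 0.2 or 0.8 | 88.6 / 96.7 | 87.1 / 94.0 | 93.8 / 95.1 |
| 0.3 or 0.7 | 84.0 / 92.4 | 91.0 / 94.0 | 93.5 / 95.7 |
| 0.4 or 0.6 | 89.9 / 98.2 | 91.9 / 95.3 | 94.1 / 94.1 |
| 0.5 | 89.1 / 97.9 | 95.1 / 95.1 | 93.5 / 93.5 |
| Average, 0.1–0.9 | 86.8 / 95.6 | 90.7 / 95.4 | 93.5 / 95.1 |

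The lowest coverage over 0.1–0.9 at n=17 is 79.7% for Wald and 91.9% for Wilson. Wald is below 90% over 28% of that range at n=17, and over 3% at n=50.

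**Degenerate and impossible limits at n = 17**

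- 17/17: Wald 1.00 to 1.00; Wilson 0.82 to 1.00.
- 0/17: Wald 0 to 0; Wilson 0 to 0.18.
- 16/17: Wald 0.83 to 1.05; Wilson 0.73 to 0.99.
- Chance of zero width: 0.9¹⁷ + 0.1¹⁷ = 16.7% at p = 0.1 or 0.9; 2.3% at 0.2 or 0.8; 0.2% at 0.3 or 0.7; 2.1% averaged over 0.1–0.9.

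**Pairwise differences**, by joint binomial enumeration, with both rates on a 0.025-step grid over 0.1–0.9:

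- 17 vs 17: Wald averages 93.0% (minimum 86.2%, at 0.1 vs 0.9); Newcombe averages 94.9% (minimum 92.0%).
- 17 vs 17 at 0.5 vs 0.3: Wald 94.2%, Newcombe 93.8%.
- 17 vs 17 at 0.95 vs 0.85: Wald 91.3%, Newcombe 98.1%, Miettinen-Nurminen 97.1%.
- 50 vs 50: Wald averages 94.3% (minimum 92.7%); Newcombe averages 95.0%.

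**The case against.** The case for leaving the text alone is mainly about consequence. The analyses are descriptive, with no test, multiplicity scheme or decision rule. The rebound cohort is an add-on with no precision target. SAP 6.1.1 requires counts as well as proportions, so a reader could recompute unstratified intervals for single arms and for differences, and a 17/17 result shown as 100% to 100% is visibly degenerate. All of this stands, and it limits the seriousness of the point. It does not make the label right: an interval reported as 95% should cover about 95%, and the report should not rely on readers to repair it.

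The second line is that the worst cases carry the argument. In part that is fair. In the middle of the range Wald does well: at n=50 it equals Wilson at 0.4 and 0.5, at n=17 it equals Wilson at 0.5, and for a 17 vs 17 difference at 0.5 vs 0.3 it is slightly nearer nominal than Newcombe. The 86.2% minimum for differences needs an 80-point gap between durations of the same drug, and Wald falls below 90% in only 3.7% of the grid. The argument for changing the difference intervals is therefore weaker than that for the single-arm intervals.

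Third, the 91% average depends on the range chosen. At n=17 it is about 83% over almost the whole of 0 to 1 and 91.6% over 0.2–0.8. Every one of these is below 95%.

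**Conclusion.** The concern holds. In the rebound population the specified single-arm interval falls clearly short of its label: 90.7% on average at n=17 for true proportions spread evenly over 0.1–0.9, lower if fewer are enrolled or evaluable (86.8% at an assumed 10 per arm), and zero width at 0% or 100% observed. Rebound differences are mildly affected, 93.0% on average.

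In the main population the single-arm shortfall is about 1.5 points on average and about 7 points at 0.1 or 0.9; p = 0.1 is the first row of Table 2. Main-population differences are close to nominal, so the comparison of treatment durations there is essentially unaffected. This should be corrected, but it threatens no conclusion of the study. The result rests on binomial sampling, on the arm sizes above, and on the plan's own range of proportions.

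**What to change.** In SAP 6.1.1 and Appendix 1:

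1. Specify Wilson score intervals for single-arm proportions in both populations.
2. Specify unstratified Newcombe or Miettinen-Nurminen intervals for pairwise differences in the rebound population.

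Both are standard software options and need no new data. Nothing in the protocol has to change; the SAP version history shows the primary-endpoint methodology was itself added to 6.1.1 in version 2. There are two costs. Reported intervals would no longer correspond exactly to the Wald-based Table 2: at n=50 the full Wilson width is 0.170 against 0.166 at p = 0.1, 0.218 against 0.222 at 0.2, and 0.267 against 0.277 at 0.5. Rebound difference intervals also become conservative when both rates are near 0 or 1.

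A separate option, for precision and not coverage, is to report main-population differences stratified by the randomization factor (Mantel-Haenszel). The SAP should then state which stratum value is used. For subgroups, SAP 6.3 says "Participants will be analyzed according to the category as determined by the CRF data and not according to the category selected at randomization" when the two differ; nothing equivalent is stated for the primary comparison.

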5. GENERAL METHODOLOGY AND CONVENTIONS

5.1. Hypotheses and Decision Rules

No formal hypothesis testing will be performed for this study.

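### No planned analysis adjusts the primary between-arm differences in the main population for baseline nasopharyngeal (NP) viral RNA; a prespecified adjusted difference beside the crude one could narrow the intervals at almost no cost

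*SAP*

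**What the plan says.** The between-arm analysis of the primary endpoint is one sentence in SAP 6.1.1: "The difference in proportions for the primary endpoint and associated 95% CI will be calculated for each pairwise comparison of the treatment arms". SAP Appendix 1 gives the method as "95% CI for proportion and the difference in proportion using binomial distribution normal approximation". Neither place names a stratum or covariate, and Protocol 9.3.2.2 plans the same pairwise differences, also without adjustment.

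Two baseline factors are available:

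- **Randomization stratum.** In the main population, "randomization will be stratified by those who are considered immunocompromised solely based on corticosteroids or TNF blocker use" (SAP 2.3). Enrollment to the yes stratum is capped at about 25%. The rebound population is not stratified.
- **Baseline NP viral RNA.** SAP 3.4 defines a baseline window and allows for a missing value.

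For the primary endpoint, both factors appear as subgroup splits in SAP 6.3 (RNA cut at 10^4 and at 10^7 copies/mL). RNA is also used in SAP 6.1.2 item 3, which drops participants below the LLOQ at baseline. SAP 6.4.1 tabulates baseline viral load by arm. None of these produces an adjusted overall difference.

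The study is descriptive: "No formal hypothesis testing will be performed for this study" (SAP 5.1), and "no power calculation was carried out to assess the number of participants required for each treatment arm" (SAP 2.4).

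**The concern.** With no test and no power target, what the trial can say about comparing durations rests on point estimates and their intervals. At 50 per arm those intervals are close to plus or minus 20 points. If a measured baseline variable predicts the outcome, leaving it out of the contrast gives up precision that needs no further data.

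Baseline RNA is a natural candidate, because the endpoint is the same assay falling below 2.0 log10 copies/mL and staying there. Its spread may be wide. Main-population entry sets no limit on symptom duration, SAP 6.3 has a category beyond 30 days since first symptom, and participants already below the LLOQ stay in the primary analysis.

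There is also a point of interpretation. The baseline table will show any RNA imbalance between arms, but the plan offers no prespecified way to judge its effect on the overall contrast. An adjustment chosen after unblinding would be less credible.

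**Working it through.** **1. The plan's own figure.** SAP Table 2 (n = 50) reproduces with 1.96 × sqrt(p(1−p)/50). At p = 0.1, 0.2, 0.3, 0.4 and 0.5 this gives 0.083, 0.111, 0.127, 0.136 and 0.139. These are half-widths. The full width at p = 0.5 is 2 × 0.1386 = 0.277, so the statement that "the width of the 95% CI does not exceed 14" percent holds only as plus or minus 14 points. This labelling matter is separate from the present point. Table 2 covers one arm; the documents state no precision for a difference.

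**2. Crude pairwise difference.** The half-width is 1.96 × sqrt(2p(1−p)/50):

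- p = 0.5: 1.96 × 0.100 = 0.196
- p = 0.3 or 0.7: 1.96 × sqrt(0.42/50) = 0.180

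**3. Stratum alone.** With stratum share w and between-stratum risk difference D, the variance removed is R² = w(1−w)D²/(p(1−p)), and the half-width is multiplied by sqrt(1−R²). With w = 0.25 (the cap), p = 0.5 and D assumed:

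| D | R² | Half-width |
|---|---|---|
| 0.1 | 0.0075 | 0.196 → 0.195 |
| 0.2 | 0.030 | 0.196 → 0.193 |
| 0.4 | 0.120 | 0.196 → 0.184 |

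The stratum matters only if it is very strongly prognostic.

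**4. Stratum plus baseline RNA.** This was simulated with 2,500 trials per setting: 50 versus 50, stratum balanced by design, logistic model with arm, stratum and continuous baseline RNA, standardized to a risk difference. All odds ratios (OR) are assumptions.

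| RNA OR per SD | Stratum OR | Half-width, p = 0.5 | Half-width, p = 0.7 |
|---|---|---|---|
| Crude analysis | – | 0.194 | 0.178 |
| 1 | 1 | 0.196 | 0.179 |
| 1 | 2 | 0.194 | 0.178 |
| 1.5 | 1.5 | 0.192 | 0.176 |
| 2 | 2 | 0.184 | 0.170 |
| 3 | 2 | 0.174 | 0.161 |

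At p = 0.5 the narrowing is 1 − 0.184/0.194 = 5% for OR 2 and 1 − 0.174/0.194 = 10% for OR 3. The corresponding relative efficiencies are 1.10 and 1.25. Crude coverage was 0.934 to 0.949 in every setting.

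The plan's stated range for the success proportion is 0.1 to 0.5. At its lower end (p = 0.1 to 0.3) the ratio of adjusted to crude SE was 0.99 to 1.00 for OR 1.5 and 0.96 to 0.99 for OR 2. For OR 3 it was 0.97, 0.92 and 0.91 at p = 0.1, 0.2 and 0.3. These ratios carry Monte Carlo error of about 0.01 to 0.02.

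**5. Chance imbalance in baseline RNA.** The standardized mean difference between two arms of 50 has SD sqrt(1/50 + 1/50) = 0.20. The probability that it exceeds 0.2 SD in either direction is 2 × (1 − Φ(1)) = 0.32, and its 95% range is ±0.39 SD. The shift in the crude difference for a 0.2 SD imbalance is about 0.2 × ln(OR) × the mean of π(1−π), where π is each participant's success probability. At overall p = 0.5:

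- OR 1.5: 0.2 × 0.405 × 0.240 = 0.019
- OR 2: 0.2 × 0.693 × 0.225 = 0.031
- OR 3: 0.2 × 1.099 × 0.200 = 0.044

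That is about 2 to 4 points, against a half-width of 19.

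**The case against.** The strongest reply is that nothing here is wrong. The crude difference is unbiased under randomization, its interval already allows for chance imbalance, coverage is near nominal, and the study makes no test. All of this stands. A reader might infer from the missing adjustment that the primary contrasts are biased or invalid; they are not.

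A reader might also infer that the stratum is open to chance imbalance. In the main population it is not, because randomization is stratified on it. Step 3 shows that adjusting for it alone gains almost nothing at moderate strengths. The rebound population has no stratum.

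The gain from baseline RNA depends on a prognostic strength that the documents do not give. One log-linear effect across recent and long-standing infection is not self-evident. This also stands, and it is why the size is given as a range that includes zero.

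The objection does not remove the gap. The baseline-below-LLOQ exclusion answers a different question and loses participants. Subgroup tables do not adjust the overall contrast, and a baseline table shows an imbalance without estimating its effect.

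**Conclusion.** The point holds for the main study population as one of efficiency and interpretation, not as an error. No planned analysis adjusts the primary between-arm difference for baseline NP RNA or the stratum. At 50 per arm, adjustment would narrow the 95% CI by about 5% to 10% if RNA has an odds ratio of 2 to 3 per SD and success is near 0.5. It would narrow it less at lower success proportions. If neither factor is prognostic there is a trivial loss (0.194 to 0.196 at p = 0.5). Almost all of the gain comes from RNA. The prognostic strengths are assumptions throughout.

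Two further readings go too far. The first is that the adjusted estimate should replace the planned contrast. The crude difference is specified in Protocol 9.3.2.2, and Protocol Section 9 calls for an amendment when a primary analysis is changed in a major way. Nothing found here shows that replacement is needed. The second is that the rebound population should be adjusted too. With up to 50 participants over three arms (about 17 each, possibly fewer), a logistic model may be unstable.

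**What to change.** Add one supplementary analysis to SAP 6.1.2 and Appendix 1, for the main population only. For each pair of durations, report a risk difference with 95% CI from a logistic model with arm, randomization stratum and continuous baseline log10 NP RNA. Standardize it over the analysis set and show it beside the crude difference. Specify the following:

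- **Stratum:** use the value as randomized, with the CRF value as a check. SAP 6.3 uses the CRF value for subgroups, so the choice must be explicit.
- **Baseline below LLOQ or undetectable:** keep the coding in SAP 5.3 (1.7 and 0.0) and add an indicator for undetectable, so that the value 0.0 does not drive a linear term.
- **Missing baseline:** state a fill-in for the covariate only, as an explicit exception to the SAP 5.3 rule that missing RNA is not imputed. Outcome data remain unimputed.
- **Rebound population:** no adjusted analysis required.

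The cost is one extra model and one table, with no new data. Because the planned contrast is unchanged, the addition does not call for a protocol amendment under Protocol Section 9. The only statistical downside is the trivial loss of precision if RNA proves not to be prognostic.
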